A total of 303 AHF subjects received at least 1 dose of omecamtiv mecarbil and an equal number received placebo. No statistically significant difference was observed in dyspnea symptom response (primary efficacy endpoint) between omecamtiv mecarbil treatment groups and the pooled placebo group.

Major cardiovascular events were adjudicated by an independent, academic committee in ATOMIC-AHF (Duke Clinical Research Institute Clinical Events Classification (CEC) Committee. Adverse events (58% vs. 63%), serious adverse events (21.8% vs. 23.1%), deaths (2.6% vs. 3.3%), and rehospitalization within 30 days (9.6% vs. 12.2%) were similar between the pooled omecamtiv mecarbil group and the pooled placebo group, respectively. At the 6 month vital status assessment, 38 (12.5%) subjects in the omecamtiv mecarbil groups died compared with 39 (12.9%) subjects in the placebo groups. There were a limited number (10) of positively adjudicated post-randomization myocardial infarctions and a small numeric imbalance was noted in the omecamtiv

Approved

mecarbil treated groups (total of 7) compared with 3 in placebo groups (2.3% vs. 1%, respectively). Five of the adjudicated myocardial infarctions in omecamtiv mecarbil-treated subjects occurred in cohort 3, however, 2 occurred more than 7 days after completion of drug infusion and 1 occurred subsequent to a percutaneous coronary intervention. The overall incidence of reported supraventricular tachyarrhythmias (standard MedDRA query [SMQ]) was less (3.6% vs. 6.6%) on omecamtiv mecarbil than on placebo and, within each cohort, rates were lower in the omecamtiv mecarbil group than the placebo group. The overall incidence of ventricular tachyarrhythmias (SMQ) was similar (5.3% omecamtiv mecarbil, 5.9%, placebo). For further details on the clinical experience with omecamtiv mecarbil please consult the Investigator's Brochure.

2.2.2.3 Study in Japanese Subjects

Study 20120255 (CY 1211) was a phase I single center, placebo-controlled, double-blind study comparing the PK of omecamtiv mecarbil between healthy Japanese and Caucasian volunteers. In a 3-period crossover design, 36 subjects (18 Japanese and 18 Caucasians) received 3 separate treatments with at least a 7-day washout between each dosing period. Volunteers received in succession an IV infusion (4 hour) of omecamtiv mecarbil or placebo, multiple 25 mg doses of a MR oral formulation of omecamtiv mecarbil or placebo over 7 days, and a single 50 mg dose of a MR oral formulation of omecamtiv mecarbil or placebo. There were no clinically meaningful differences observed in the PK of omecamtiv mecarbil between Japanese and Caucasian healthy volunteers and all doses of omecamtiv mecarbil in CY 1211 were well tolerated.

2.3 Rationale

Omecamtiv mecarbil is being developed as an adjunctive therapy for subjects with HF with reduced ejection fraction ($\leq 40\%$) who are already taking a beta-blocker and an ACE inhibitor and/or angiotensin receptor blocker (ARB), unless not tolerated. Targeting myocardial contractility in subjects with systolic dysfunction would appear to be a rational therapeutic approach to preserve cardiac output, to attenuate the compensatory mechanisms including neurohormonal activation, and to prevent or even reverse ventricular remodeling, which ultimately could translate into clinical benefits for HF patients ([Hasenfuss and Teerlink, 2011](#)).

Historically, development of heart failure drugs has required careful assessment of the balance of benefit:risk in large phase 3 clinical outcomes studies because there is no well-established validated surrogate endpoint in HF for clinical outcomes. Direct

increase of cardiac function can positively impact clinical outcomes in patients with left ventricular systolic dysfunction as evidenced by the efficacy of cardiac resynchronization therapy (CRT) in HF patients with systolic dysfunction (Moss et al, 2009). Omecamtiv mecarbil is a cardiac myosin activator that has dose-dependent and concentration-dependent effects on cardiac function at plasma concentrations that appear generally well tolerated by subjects with stable chronic systolic HF (Cleland et al, 2011).

The ongoing Study 20110151 (COSMIC-HF) is a global phase 2, randomized, double-blind, placebo-controlled study in subjects with chronic stable HF and systolic dysfunction. This study was designed to compare 3 oral MR formulations in 2 cohorts (escalation phase) of 25 mg BID and 50 mg BID for 7 days to select the most suitable formulation for further study in the dose ranging expansion phase (25 mg BID and 50 mg BID of a single oral MR formulation compared with placebo over 20 weeks of treatment with echocardiographic evaluations). The escalation phase of the study has completed. Following review of PK and safety data from a total of 96 subjects, a single oral MR formulation, MR-F1, was selected for use in the COSMIC-HF expansion phase. Enrollment is complete and the MR-F1 formulation is currently being evaluated at 2 dose levels (25 mg and 50 mg BID) in approximately 450 subjects.

Prior to initiation of subject enrollment into this study (Study 20120227) results from the planned Japanese phase 1 study 20150134, which include PK and safety assessments of repeated 25 mg BID, 37.5 mg BID, and 50 mg BID oral dosing, will be reviewed. It is expected that Study 20150134 will confirm the doses selected are appropriate to be studied in this phase 2 study (Study 20120227).

Study 20120227 will enroll approximately 80 subjects and randomize them to doses of omecamtiv mecarbil (25 mg, 37.5 mg, or 50 mg BID), or placebo. Simulated omecamtiv mecarbil exposures in subjects with low body weight, defined as less than 58 kg based on the median body weight distribution of Japanese subjects with HF, were approximately 25% to 35% higher compared with exposures in non-Japanese HF subjects with a higher body weight, defined as greater than 82 kg based the median body weight of subjects with HF in the ATOMIC-AHF and COSMIC-HF studies (Table 1).

Table 1. Comparison of Omecamtiv Mecarbil Steady State C_{max} and AUC Following BID Dosing of MR-F1 Tablets in Healthy Japanese Subjects

BID Dose (mg)	Simulated Japanese		Simulated Non-Japanese	
	$C_{max,ss}$ (ng/mL)	AUC _{ss} (ng*hr/mL)	$C_{max,ss}$ (ng/mL)	AUC _{ss} (ng*hr/mL)
25	277 [252] (129)	2759 [2501] (1305)	211 [193] (94)	2115 [1918] (962)
37.5	461 [418] (214)	4613 [4171] (2185)	351 [319] (155)	3521 [3201] (1585)
50	614 [557] (286)	6143 [5539] (2929)	469 [427] (209)	4707 [4265] (2130)

Data presented as mean [median] (standard deviation); AUC_{ss} = area under the curve, steady state; C_{max} = maximum plasma concentration; HF = heart failure; BID = twice daily

Though the results of the completed phase 1 Study 20120255 showed that systemic clearance in Japanese and Caucasian subjects was not statistically significantly different, and that the body weight adjusted clearance was essentially identical, this study will include an additional tablet strength of 37.5 mg BID to further explore PK and PD parameters with chronic repeated oral dosing.

2.4 Clinical Hypotheses

No formal hypothesis testing will be performed. PK parameters following chronic dosing (BID for 16 weeks) will be estimated.

3. EXPERIMENTAL PLAN

3.1 Study Design

This is a double-blind, randomized, placebo-controlled, multicenter, phase 2 study in Japanese HF subjects to evaluate 16 weeks of administration of oral MR omecamtiv mecarbil formulation at 3 dose levels (25 mg BID, 37.5 mg BID, and 50 mg BID), compared with placebo. Potential subjects will be screened to assess their eligibility to enter the study within 30 days prior to enrollment. Subjects are eligible for screening if they have chronic stable HF and reduced ejection fraction. Subjects may also be screened in the hospital setting once they have recovered and are considered clinically stable by the investigator. Subjects must be outpatients at the time of randomization.

Approximately 80 Japanese subjects with chronic stable HF with reduced ejection fraction will be randomized 1:1:1:1 to receive omecamtiv mecarbil either 25 mg BID dose (n=20), 37.5 mg BID dose (n=20), 50 mg BID dose (n=20) or placebo (n=20) on an outpatient basis. Subjects randomized to 37.5 mg BID target dose and 50 mg BID target dose will initiate administration at 25 mg BID and will be up-titrated to 37.5 mg BID or

50 mg BID at the week 4 visit based on steady state concentration prior to investigational product (IP) administration ($C_{predose}$) result from week 2. Subjects who do not have a week 2 PK value in time for dose adjustment at the week 4 visit will be up-titrated at week 8 based on the steady state $C_{predose}$ result from week 2, if available. Subjects will be up-titrated at the week 4 or week 8 visits only if the week 2 $C_{predose}$ is < 200 ng/mL. Subjects with a week 2 $C_{predose} \geq 200$ ng/mL (or not available at week 8) will continue at 25 mg BID for the remaining of the study. Subjects randomized to placebo or to 25 mg BID will receive the assigned IP throughout the study. IP compliance will also be monitored. PK analysis and dose assignment will be blinded to the study team. To maintain blinding, all subjects will receive new IP supply at the week 4 and week 8 visits. The study includes transthoracic echocardiographic assessments (screening, week 8, and week 16). Enrollment of subjects with atrial fibrillation/flutter at the time of screening will be limited to approximately 20% of planned enrollment. Randomization will be stratified by presence or absence of atrial fibrillation/flutter via the interactive voice response system/interactive Web response system (IVRS/IWRS). An independent DMC will perform regular formal unblinded review of the accumulating study data. An independent CEC will adjudicate deaths, all hospitalizations, and selected nonfatal cardiovascular (CV) events (including possible MI or ischemia). The end of study (EOS) visit will be performed 4 weeks after the last dose of IP (Week 20 +3 days).

Vital signs, physical examinations, ECGs, Adverse Event/Serious Adverse Event assessments, clinical laboratory evaluations (see [Table 3](#)), and collection of concomitant medications will be performed at screening and at specified times per the Schedule of Assessments ([Table 2](#)). The overall study design is described in a [study schema](#) at the end of the protocol synopsis section.

The study endpoints are defined in [Section 10.1.1](#).

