2.2.2.1 Studies in Healthy Volunteers

CY 1111, a first-in-human clinical study with omecamtiv mecarbil, was a randomized, double-blind, placebo-controlled, 4-period crossover, dose escalation study designed to evaluate the safety, tolerability, and PK/PD profile of omecamtiv mecarbil administered IV to healthy male volunteers ([Teerlink et al, 2011](#)). This study included a total of 33 subjects who received infusions of omecamtiv mecarbil at doses ranging from 0.005 mg/kg/hr to 1.0 mg/kg/hr for up to 6 hours. The exposures of omecamtiv mecarbil, as measured by area under the curve (AUC) and maximum observed concentration (C_{max}), were approximately dose proportional, with an AUC of 159 (57 standard deviation) ng•hr/mL for treatment administered at an infusion rate of 0.005 mg/hr/kg and 30400 ng•hr/mL when administered at a rate of 1 mg/hr/kg; corresponding C_{max} values for those administration rates were 8.70 (2.20) ng/mL and 1340 ng/mL. The mean clearance ranged from 125 to 207 mL/hr/kg and the mean half life ranged from 17.1 to 23.2 hours and increased slightly with increasing doses. The mean steady state distribution volume was dose independent and ranged from 3.6 to 5.2 L/kg. At the dose of 0.5 mg/kg/hr over 6 hours, the mean (standard deviation [SD]) C_{max} was 905 (183) ng/mL. Across the dosing levels evaluated in CY 1111, omecamtiv mecarbil infusions demonstrated generally linear PK with dose-proportional increases in C_{max} . Concentration-dependent PD effects on cardiac function as measured by echocardiography were observed. These PD effects included statistically significant placebo corrected increases from baseline in SET, Doppler-derived stroke volume, left ventricular ejection fraction (LVEF), and fractional shortening.

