6.2.1.1 Dosage, Administration, and Schedule

Eligible outpatient subjects will be randomized and will initiate administration of IP (omeamtiv mecarbil or placebo). Day 1 is defined as the calendar day when treatment with IP is initiated. The first administration of IP should be on the day of randomization but not later than 5 calendar days after randomization. The time when ingestion of the first dose of IP is completed is defined as Time = 0 hours. Baseline procedures must be completed before initiation of IP and can be performed on the same day.

IP will be administered orally BID in the morning and evening by the subjects and can be taken under fasted or fed conditions. IP will be swallowed whole (not chewed) and taken with water as instructed in the IPIM. Administration of each morning and evening dose is to be taken at approximately the same time of day (12 ± 3 hours from the most recent previous dose). If IP cannot be taken or has not been taken within this window, the dose should be recorded as missed and the next dose should be taken at the regular time.

Administration of IP will start with the morning dose on day 1 and will end with the morning dose on the day of the subject's week 16 visit. The quantity, date and time, lot number, and bottle number of investigational product is to be recorded on each subject's eCRF.

6.2.1.2 Rules for Withholding Investigational Product due to Myocardial Ischemia or Infarction, Abnormal Blood Pressure or Heart Rate

Omecamtiv mecarbil may result in signs and symptoms of myocardial ischemia or infarction, as described in Section 7.1 of the Investigator's Brochure (eg, increases in HR, dizziness, dyspnea, hypotension, chest discomfort or pain, ST-segment depression on ECG, and/or elevations in troponin I or T). If a subject reports clinical signs or symptoms suggestive of myocardial ischemia or infarction, and/or experiences changes in BP or HR, withholding of IP should be considered. No antidote to omecamtiv mecarbil exists. Standard medical therapies should be used in the presence of signs or symptoms of myocardial ischemia.

The following are mandatory rules for withholding IP:

- The subject experiences clinical signs or symptoms, including ECG changes, consistent with myocardial ischemia or infarction as determined by the investigator
- The subject experiences a symptomatic decrease in systolic BP on 2 successive measurements

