^j Vital signs and PK samples at predose, at 2 hours \pm 30 minutes; 4 hours \pm 30 minutes; 6 hours \pm 30 minutes; 8 hours \pm 30 minutes after IP administration in the morning (0 h = start of IP); echocardiogram performed as close as possible after the collection of PK sample at 2 hours \pm 30 minutes following IP administration.

^k Vital signs and PK samples at predose and at 2 hours \pm 30 mins following IP administration. Echocardiogram should be performed as close as possible after the collection of PK sample at 2 hours \pm 30 minutes following IP administration.

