10. STATISTICAL CONSIDERATIONS

10.1 Study Endpoints, Analysis Sets, and Covariates

10.1.1 Study Endpoints

10.1.1.1 Primary Endpoints

- Concentrations prior to administration (Cpredose) of omecamtiv mecarbil at weeks 2, 4, 12, and 16, and area under the curve (AUC) at week 8

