6.4 Other Study Related Definitions

Analytical Study Week Assignments

Analytical windows will be used to assign parameters to study days/weeks. The algorithm is provided in [Appendix A](#).

Actual Treatment Group

A subject's actual treatment group is the randomized treatment group, unless the subject receives the same treatment throughout the study that is different to the randomized treatment group assignment, in which case the actual treatment group is the treatment received. For subjects randomized to omecamtiv mecarbil 37.5 mg BID and 50 mg BID, the actual treatment groups: 25 mg (Not up-titrated to 37.5 mg), 25 mg (Up-titrated to 37.5 mg) and 25 mg (Not up-titrated to 50 mg), 25 mg (Up-titrated to 50 mg) respectively, includes only those subjects who have a minimum IP exposure period of 25 days. Titration status groups may be used in select outputs and these four actual treatment groups should only be compared to each other. The omecamtiv mecarbil

Overall 37.5 mg BID, and Overall 50 mg BID actual treatment groups include all the subjects included in the omecamtiv mecarbil 37.5 mg BID, and 50 mg BID randomized treatment groups respectively.

Investigational Product (IP)

IP includes Omecamtiv Mecarbil 25 mg BID, 37.5 mg BID, and 50 mg BID and Placebo BID.

IP Dose Administered (mg)

From IP administration eCRF, number of tablets administered from each box is # dispensed - # lost or missing - # returned. If any of these numbers is missing, the sum of tablets reported on the IP administration eCRF for the same box will be used. IP dose administered is the sum of all the tablets' dose from all boxes dispensed.

IP Compliance (%)

Total IP dose administered divided by the total planned dose (223 tablets), multiplied by 100.

IP Exposure Period in Days

((Last IP administration date in the IP administration form – date of Study Day 1) + 1.

IP Exposure Period in Weeks

((Last IP administration date in the IP administration form – date of Study Day 1) + 1) / 7.

Study Exposure Period in Days

For each randomized subject, Study Exposure Period = (EOS Date – Randomization Date) + 1.

Study Exposure Period in Weeks

For each randomized subject, Study Exposure Period = ((EOS Date – Randomization Date) + 1) / 7.

Treatment-Emergent Adverse Event (TEAE)

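### Subjects up-titrated late, at the week 8 visit, have the only AUC profile at that same visit, and no analysis rule keeps these profiles out of the 37.5 and 50 mg summaries.

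*Protocol*

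**What the plan says.** **Titration.** Protocol 3.1 (repeated in the synopsis, 5.1, Table 2 footnote g and SAP 3.1) starts the 37.5 and 50 mg arms on 25 mg BID and plans the step up at week 4. Subjects whose week 2 value is not ready "in time for dose adjustment at the week 4 visit will be up-titrated at week 8 based on the steady state" predose concentration. The condition is the same at both visits: "Subjects will be up-titrated at the week 4 or week 8 visits only if the week 2" predose concentration is below 200 ng/mL.

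**Profile.** Protocol 10.1.1.1 names week 2, 4, 12 and 16 predose concentrations "and area under the curve (AUC) at week 8" as primary endpoints. Table 2 footnote j puts samples at predose and at 2, 4, 6 and 8 hours, each post-dose sample within "30 minutes after IP administration in the morning (0 h = start of IP); echocardiogram performed as close as possible" after the 2-hour sample. Week 16 has only predose and 2-hour samples. SAP 6.3 takes the AUC over 8 hours at week 8.

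**Supply.** All subjects receive new supply at week 8 and are dosed on site that day (Protocol 3.1 and 7.4). Neither document says which supply the morning dose comes from; dispensing detail is left to the Investigational Product Instruction Manual (IPIM).

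**Grouping.** The protocol synopsis and 10.5.1 group by randomized assignment. SAP 10.5 uses actual doses and summarizes by *dose level*, which it does not define. SAP 6.4 sorts titration-arm subjects into up-titrated or not; each group "includes only those subjects who have a minimum IP exposure period of 25 days".

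**The concern.** The study estimates PK after chronic dosing, and the week 8 AUC is the only AUC it will have. Subjects titrated at week 4 have about 28 days on the target dose by then. Subjects titrated at week 8 have none, or one dose. If their profiles are pooled into a 37.5 or 50 mg summary, the estimated exposure at that dose is too low, and no later serial profile can replace them. Cmax and tmax come from the same samples. The Cmax/Cpredose ratio could also set a predose sample at 25 mg against a peak after a higher dose. The week 8 echocardiogram follows the same dose.

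No rule catches these subjects. The SAP's PK analysis set (SAP 7.1) has no exclusion for them. The modified set in Protocol 10.1.2 covers significant deviations and missing key dosing or sampling data, and a planned week 8 titration is neither. The filter in SAP 6.4 counts total days on investigational product, not days on the target dose, so a subject titrated at week 8 passes it.

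**Working it through.** The plan gives no figure for this point. Its nearest figure, Protocol Table 4, reproduces as 1.96 × SD / √19 (17.99 for SD 40, 40.47 for SD 90), which confirms only the planned 19 evaluable subjects per arm.

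**Inputs**
- Simulated Japanese mean steady-state AUC (Protocol Table 1): 2759, 4613 and 6143 ng·hr/mL at 25, 37.5 and 50 mg BID.
- Half-life (Protocol 2.2.2.1): "the mean half life ranged from 17.1 to 23.2 hours". This is intravenous dosing in healthy men, so its use here is an assumption.
- Dosing interval: 12 hours.

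Table 1 is more than dose-proportional from 25 mg: 4613/2759 = 1.672 against a dose ratio of 1.5, and 6143/2759 = 2.227 against 2. Protocol 2.2.2.1 describes generally linear PK, so I give results under both sets of ratios.

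**Case A: the profile dose is still 25 mg.** Shortfall = 1 − AUC(25)/AUC(target).
- 37.5 mg: 1 − 25/37.5 = 33% (proportional); 1 − 2759/4613 = 40% (Table 1).
- 50 mg: 1 − 25/50 = 50%; 1 − 2759/6143 = 55%.

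**Case B: the profile dose is the first target dose.** By superposition, AUC = AUC(25) + f × [AUC(target) − AUC(25)], with f = 1 − 2^(−12/t½). This gives f = 0.385 at 17.1 h and 0.301 at 23.2 h. With one compartment and rapid input, f is the same at every time in the interval, so it applies to the 8-hour AUC too. Slower modified-release absorption would lower f.

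| Target | Ratios used | Shortfall, t½ 17.1 h | Shortfall, t½ 23.2 h |
|---|---|---|---|
| 37.5 mg | proportional | 20.49% | 23.29% |
| 37.5 mg | Table 1 (AUC 3473; 3318) | 24.71% | 28.08% |
| 50 mg | proportional | 30.74% | 34.94% |
| 50 mg | Table 1 (AUC 4062; 3779) | 33.87% | 38.49% |

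**Effect on a group mean.** The number of late results is not given. As an illustration with Table 1 ratios, each late subject among 19 lowers the mean by 40.19/19 = 2.1% (37.5 mg) or 55.09/19 = 2.9% (50 mg) in case A. In case B it is 1.3% to 1.5%, or 1.8% to 2.0%. This assumes that the other 18 are at target-dose steady state.

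**Case C: old supply, and dose level means actual dose.** The profile is a valid 25 mg steady-state value in the 25 mg level, and there is no error.

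**The case against.** The strongest reply is case C. SAP 10.5 already uses actual doses and summarizes by dose level. The titration groups in SAP 6.4 are for select outputs, and the SAP does not say that PK is one of them. So a reader might infer that late-titrated subjects are certain to be counted at 37.5 or 50 mg, and the documents do not establish that. What stands is that dose level is undefined, SAP 10.1 points to Section 7 for grouping, SAP 7.1 gives none for PK, and the protocol groups by randomized dose. The harmless reading is possible but not secured. It also fails if the profile dose comes from the new supply.

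Other stronger readings also go too far:
- *The Table 1 shortfalls are minimum values.* They are not; dose-proportional ratios give smaller ones.
- *The randomized-arm mean is biased by a known amount.* The arm is a mixture by design, since subjects at or above 200 ng/mL, or with no result by week 8, stay on 25 mg. The target-dose steady-state value is therefore not its reference, and the late count is unknown.
- *The spread is materially inflated.* Mixing 1 to 4 late profiles into 20, with Table 1 SDs for 25 mg profiles and constant CV for first-dose profiles, changes the SD by only −2% to +3%. The CV in the 50 mg arm rises from 48% to at most 55%.
- *The protocol contradicts itself on supply.* It is silent, and the IPIM may settle the matter.

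It is also fair that the study is descriptive and that individual concentration data will be tabulated.

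**Conclusion.** The point holds in limited form. A subject titrated at week 8 cannot contribute a steady-state AUC at 37.5 or 50 mg, and the stated rules allow the profile to be summarized as if it did. Such a profile would understate the target-dose AUC by about 33% to 40% (37.5 mg) or 50% to 55% (50 mg) if the subject is still on 25 mg. If it follows the first higher dose, the shortfall is roughly 20% to 28% or 31% to 38%. These sizes rest on linear superposition, half-lives from intravenous dosing, and AUC ratios between dose-proportional and Table 1.

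Only subjects in the two higher arms are affected, and only if their week 2 result is late, available by week 8 and below 200 ng/mL. They may be few or none. A reader might infer that these subjects never provide target-dose data. That is not so: the week 12 and 16 predose concentrations come about 4 and 8 weeks after a week 8 titration, and neither they nor the week 16 SET endpoint is affected. The change is worth making because the week 8 AUC is a primary endpoint with no later replacement.

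**What to change.** 1. In SAP 10.5, define dose level for the week 8 AUC, Cmax, tmax and Cmax/Cpredose summaries as the dose taken to steady state before the profile. Exclude week-8-titrated subjects from the 37.5 and 50 mg summaries and report them separately, or under 25 mg where the recorded bottle shows a 25 mg site dose. Protocol 6.2.1.1 already requires that the "lot number, and bottle number of investigational product is to be recorded on each subject's eCRF".
2. In SAP 6.4, flag titration at week 4 against week 8. Treat week-8-titrated subjects as not yet up-titrated for the week 8 PK and week 8 echocardiogram summaries only. Time-varying status for all safety records would split subjects across adverse event tables and is not needed.
3. The sponsor should reconcile the protocol passages on week 8 titration, new supply and on-site dosing so that it is clear which supply the profile dose comes from. Which one it should be is for the sponsor to decide.

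Items 1 and 2 need SAP wording and data already collected; item 3 is a protocol clarification. The cost is that the few late-titrated subjects drop out of the target-dose AUC summary, which slightly reduces its precision.
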